2.3.2.2 Perivascular/vascular mineralization

Minimal to mild perivascular/vascular mineralization in kidney, reproductive tract and thyroid were seen in 2- and 4-week minipig toxicology studies at ≥ 15 mg/kg/q4d.

In the ongoing phase 1 study in healthy volunteers, no changes were observed in kidney function markers (e.g., eGFR) and no abnormalities were seen in urine dipstick parameters (protein, blood, glucose, ketones, bilirubin, urobilinogen, pH, leukocyte esterase, specific gravity). There was no change in cardiovascular parameters (blood pressure, ECG) or joint AE pointing to mineralization. There was no change in serum calcium. Measurement of PPi levels in serum in cohorts 1-4 from the FIH study (where single doses of 0.1, 0.3, 1 and 2 mg/kg TIN816 were given IV) showed a dose dependent and reversible reduction (cleavage) of PPi with maximum effect reached within hours post dose. PPi data in cohorts 1-4 suggest a similar effect of TIN816 on PPi concentrations compared to the ex vivo IL-1 β assay.

Comparable duration of low PPi levels was observed in minipig at the no observed adverse effect level (NOAEL) while mineralization was only seen following low PPi levels for at least 35 days. Of note, the minipig is considered a highly sensitive species to vascular calcification

compared to rats or cynomolgus monkeys. In the absence of effect on phosphorus and calcium, this low level of PPi for a duration of 2-3 weeks is unlikely to lead to vascular calcification; however, plasma calcium, phosphorus and inorganic pyrophosphate level will be monitored (see Investigator's brochure).

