9.2 Statistical analyses

9.2.1 General considerations

This study is to investigate PK, safety, tolerability and efficacy. There is no inferential analysis to be performed. The analyses will be mainly based on descriptive statistics.

Categorical data will be presented as frequencies and percentages, including quartiles. For continuous data, mean, standard deviation, median, minimum, and maximum will be presented. For PK parameters, n, mean, median, minimum, maximum, coefficient of variation (CV (%)) to mean, geometric mean, and CV(%) to geometric mean will be presented.

The baseline visit is defined at Day 1 unless specified. Parameters that are not collected at Day 1, the screening visit will be used as baseline.

For hospital-acquired AKI, a stable serum creatinine obtained in the hospital prior to AKI will be used as reference baseline: otherwise, a baseline serum creatinine is defined in the following order of preference:

1. Median value within 3 months of the hospital admission. If not available:
2. Median value between 3 and 6 months prior to hospital admission. If not available:
3. At hospital admission.

The study will exclude participants whose AKI diagnosis or AKI presence based on investigator's clinical judgement has a period longer than 48 hours prior to study drug administration because of the criticality of an early treatment for patients with SA-AKI.

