10.6.1 Specific Renal Alert Criteria and Actions and Event Follow-up

Table 10-5 Specific renal alert criteria and actions

Renal event	Actions
Confirmed serum creatinine increase of 25-49% from baseline	
 Consider causes and possible interventions Follow-up within 2-5 days
Confirmed serum creatinine increase $\geq 50\%$ from baseline (corresponds to KDIGO criterion for acute kidney injury)	
 Consider causes and possible interventions Repeat assessment within 24-48h if possible Consider patient hospitalization and specialized treatment
New onset dipstick proteinuria $\geq 3+$ OR Protein-creatinine ratio (PCR) $\geq 1\text{g/g Cr}$ (or mg/mmol equivalent as converted by the measuring laboratory)	
 Consider causes and possible interventions Assess serum albumin and serum total protein Repeat assessment to confirm
New onset of hematuria $\geq 3+$ on urine dipstick	
Assess and document
 
 Repeat assessment to confirm Exclude infection, trauma, bleeding from the distal urinary tract or bladder, menstruation Distinguish hemoglobinuria from hematuria Urine sediment microscopy Assess serum creatinine Consider bleeding disorder

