10.6.1.1 Follow-up of renal events

Assess and document:

Urine dipstick and sediment microscopy evidence of drug-induced nephrotoxicity (DIN): crystals, red blood cells (dysmorphic/glomerular vs. non-dysmorphic/non-glomerular), white blood cells, tubular epithelial cells.

Blood pressure and body weight.

Serum creatinine, BUN, electrolytes (sodium, potassium, phosphate, calcium) and uric acid.

Urine output.

Review and record possible contributing factors to the renal event (co-medications, other co-morbid conditions) and any additional local diagnostic procedures performed in the CRF.

Monitor patient regularly (frequency at investigator's discretion) until:

Event resolution: serum creatinine within 10% of baseline or PCR < 1g/g creatinine, or albumin-creatinine ratio < 300 mg/g creatinine

Or

Event stabilization: serum creatinine level with $\pm 10\%$ variability over last 6 months or protein-creatinine ratio stabilization at a new level with $\pm 50\%$ variability over last 6 months.

Analysis of urine markers in samples collected over the course of the DIN event.

11 References

References are available upon request

Billings FT, Shaw AD (2014) Clinical trial endpoints in acute kidney injury. *Nephron Clin Pract*; 127(1-4):89-93.

Burnstock G, Verkhratsky A (2010) Long-term (trophic) purinergic signalling: purinoceptors control cell proliferation, differentiation and death. *Cell Death Dis*; (1):1.

CDER (2005) Estimating the Maximum Safe Starting Dose in Initial Clinical Trials for Therapeutics in Adult Healthy Volunteers. <https://www.fda.gov/media/72309/download>

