2.1.1 General definitions

The term “**study treatment**” and/or “**study drug**” refers to the 2-hour study infusion drug during the study, that is TIN816 2 mg/kg.

For analysis purposes, “**Baseline**” is defined to be the last result obtained at or prior to start of study treatment (Day 1) for baseline demographics, medical history, lab values, vital signs and ECGs. Most variables will have their baseline at Day 1, unless otherwise specified. For assessments not performed at Day 1, the assessment at the screening visit or most recent assessment prior to start of study treatment will be used as baseline.

The reference creatinine baseline is defined as below.

For hospital-acquired AKI, a stable serum creatinine obtained in the hospital prior to AKI should be used as reference baseline, otherwise, baseline serum creatinine in the following order of preference:

1. Median value within 3 months of the hospital admission. If not available:
2. Median value between 3 and 6 months prior to hospital admission. If not available:
3. At hospital admission.

“Post-Baseline” is defined for analysis purposes to be any value collected after the “baseline” as defined above for analysis purposes.

The term **“study day”** is defined relative to the analysis reference date, which is the date of first administration of study treatment.

The *study day* for a scheduled or unscheduled visit on or after the analysis reference date is defined as:

Study day = (Date of Visit) – (analysis reference date) +1.

The *study day* for a scheduled or unscheduled visit before the analysis reference date is defined as:

Study day = (Date of visit) – (analysis reference date).

Thus the analysis reference date (date of first administration of study treatment) will be study day 1 and the date directly prior the analysis reference date will be study day □1 (there is no study day 0).

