Summary statistics for all laboratory data will be provided by treatment and visit/time. Shift tables using the low/normal/high/ (low and high) classification may be used, as appropriate, to compare baseline to the worst value. Where normal ranges are available, abnormalities in laboratory data will be listed by treatment group, participant, and visit/time.

Graphical displays of selected safety parameters (e.g. hematological parameters, thyroid and reproductive hormone levels) over time will be provided by treatment group.

For laboratory parameters which are lower or greater than the limit of quantification, the number and percentage of values below the lower limit of quantification (LLOQ) and above the upper limit of quantification (ULOQ) will be presented for categorical variables. For numerical presentation, the values less than LLOQ will be imputed as a value of $0.5 \times \text{LLOQ}$ and the values greater than ULOQ will be imputed as a value of $1.5 \times \text{ULOQ}$.

The frequency and percentage of participants with clinically significant abnormal laboratory values shown in [Table 2-2](#) will also be provided.

Table 2-2 **Clinically notable laboratory values**

Parameter	Conventional Alert Value	Conventional Units	SI Alert Value	SI Units
Hematology				
Red Blood Cell Count	>50% increase, >30% decrease	$\times 10^6/\mu\text{L}$	>50% increase, >30% decrease	$\times 10^{12}/\text{L}$
Hemoglobin	>50% increase, 30% decrease, or any value <7	g/dL	>50% increase, >30% decrease, or any value <70	g/L
Hematocrit	>50% increase, >30% decrease	%	>50% increase, >30% decrease	L/L
White Blood Cell Count	>50% increase, >50% decrease	$\times 10^3/\mu\text{L}$	>50% increase, >50% decrease	$\times 10^9/\text{L}$
Platelet Count	>75% increase, >50% decrease	$\times 10^3/\mu\text{L}$	>75% increase, >50% decrease	$\times 10^9/\text{L}$
Chemistry				
BUN	>50% increase	mg/dL	>50% increase	mmol/L
Creatinine	>50% increase	mg/dL	>50% increase	$\mu\text{mol}/\text{L}$
Albumin	<2	g/dL	<20	g/L
Glucose	>50% increase, >50% decrease, or any value <60	mg/dL	>50% increase, >50% decrease, or any value <3.3	mmol/L
Total Bilirubin	>100% increase	mg/dL	>100% increase	$\mu\text{mol}/\text{L}$
Creatine phosphokinase (CPK)	>300% increase	U/L	>300% increase	U/L
AST (SGOT)	>150% increase	U/L	>150% increase	U/L
ALT (SGPT)	>150% increase	U/L	>150% increase	U/L
Alkaline phosphatase	>100% increase	U/L	>100% increase	U/L

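### By default the Table 2-2 creatinine count compares with a value taken during AKI, so it misses a second kidney injury up to 1.5 times Day 1; Appendix 6 names no baseline and is inconsistent on either reading

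*SAP*

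**What the plan says.** **The count.** SAP 2.6.1 will report "The frequency and percentage of participants with clinically significant abnormal laboratory values shown in" Table 2-2. For creatinine the only trigger is a rise of more than 50%; BUN has the same form. Hemoglobin, glucose, sodium and potassium each add an absolute limit. The creatinine row does not state what the rise is measured from.

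**The default baseline.** SAP 2.1.1 defines baseline as the "last result obtained at or prior to start of study treatment (Day 1) for baseline demographics, medical history, lab values", vital signs and ECGs. Protocol 9.2.1 agrees: "The baseline visit is defined at Day 1 unless specified". Protocol 5.1 requires AKI at randomization, and 5.2 excludes patients already recovering.

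**A second creatinine baseline.** SAP 2.1.1 adds: "The reference creatinine baseline is defined as below". This is a stable in-hospital value before AKI or, failing that, an earlier median or the admission value. Its only stated use in the visible SAP is the baseline characteristics table (2.3.1).

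**Appendix 6 of the protocol.** Sections 10.6 and 10.6.1 set alerts at creatinine rises of 25% and 50% from an unspecified baseline. The 50% row carries the remark "corresponds to KDIGO criterion for acute kidney injury". Section 10.6.1.1 then gives "Event resolution: serum creatinine within 10% of baseline", or a urine protein alternative, and allows stabilization to be judged over the preceding 6 months. Participants are followed for 90 days.

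**The concern.** A percentage rise from baseline detects new harm well when baseline is the participant's usual state. Here the default baseline is the acute illness itself. A kidney that recovers and is injured again is compared with the first injury, and the worse the first injury, the larger the second must be before it is counted. The row therefore has a different effective threshold for each participant. With about 15 participants on TIN816 and 5 on placebo, and no stratification described, a chance difference in Day 1 severity would give the two arms different thresholds.

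Safety against placebo is the only secondary objective, so a by-arm laboratory count that is blind to late renal injury would weaken the reading of that objective.

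Appendix 6 raises a related question. Two creatinine baselines exist, and its alert and resolution rules mean different things depending on which one is used.

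**Working it through.** **Inputs.** Table 2-2: creatinine flagged above 1.5 times the comparator. Protocol Table 8-1: stage 1 is 1.5-1.9 times baseline or a rise of at least 0.3 mg/dL; stage 2 is 2.0-2.9 times; stage 3 is 3.0 times or at least 4.0 mg/dL. The documents give no creatinine data, so the values below (reference 1.0 mg/dL, Day 1 from 1.3 to 3.0 mg/dL) are assumptions for illustration.

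**Step 1: the protocol's own equivalence.** A 50% rise is 1.5 times baseline. If baseline is the reference creatinine, this is the lower bound of the stage 1 ratio, so the KDIGO remark is reproduced. If baseline is Day 1, let r = Day 1 / reference. The line is then 1.5 × r times reference, and the remark holds only if r = 1.

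**Step 2: where the Table 2-2 line falls against Day 1.** Line = 1.5 × Day 1. Largest rise from a recovered value of 1.0 that is not flagged = (1.5 × Day 1 − 1.0) / 1.0.

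| Day 1 (mg/dL) | Flagged above | Stage at that line | Largest rise from 1.0 not flagged |
|---|---|---|---|
| 1.3 | 1.95 | 1 | 95% |
| 1.5 | 2.25 | 2 | 125% |
| 2.0 | 3.00 | 3 | 200% |
| 3.0 | 4.50 | 3 | 350% |

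**Step 3: worked course.** Reference 1.0, Day 1 2.0, recovery to 1.0 by Day 14, second peak at Day 30.
- Peak 2.9: 2.9/2.0 = 1.45, so +45% from Day 1 and not flagged; 2.9/1.0 = 2.9, so +190% from recovery (stage 2).
- Peak 2.0: 0% from Day 1, +100% from recovery (stage 2), not flagged.
- Peak 3.1: 3.1/2.0 = 1.55, so +55% and flagged.

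Counting from the lowest earlier post-dose value (1.0) flags all three.

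**Step 4: other laboratory outputs in SAP 2.6.1.** By-visit summaries pool participants. Listings show individuals but are not counts. Shift tables are optional and compare baseline with the worst value as low, normal or high; a participant already high on Day 1 is high-to-high with or without a second injury.

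**Step 5: Appendix 6 on each reading.**
- *Reference creatinine.* The KDIGO remark fits. But a qualifying rise of 0.3 mg/dL is at least 25% whenever 0.3/reference ≥ 0.25, that is, for any reference up to 0.3/0.25 = 1.2 mg/dL. Such participants meet the alert on entry.
- *Day 1.* The KDIGO remark does not fit (Step 1). With Day 1 at 2.0, the 25% alert begins at 2.5, and the 10% band is 1.8-2.2, which is still 1.8-2.2 times reference (stage 1-2). With Day 1 at 3.0 the band is 2.7-3.3 (stage 2-3). A return to the AKI level qualifies, while full recovery to 1.0 literally falls outside the band.
- *Either reading.* A 6-month look-back cannot be completed within 90 days of follow-up.

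**The case against.** **The comparator is inferred.** Table 2-2 repeats Protocol Table 10-1, and Protocol 10.3.1 lets the site look at changes from baseline or from the previous visit. Against the previous visit, 1.0 to 2.9 is caught. This stands in part: Day 1 is the default and not an explicit statement in the table. But 10.3.1 describes how sites identify notable values, and the SAP does not say that its count uses the previous visit.

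**Other routes exist.** A reader might infer that late renal injury goes unreported, or that renal safety as a whole rests on this row. The documents do not support that. New AKI reported after dosing is a treatment-emergent event and is summarized. Clinically significant laboratory values must be reported as adverse events. Out-of-range values are listed, and in a study of about 20 participants a creatinine of 2.9 would be seen. On the Day 1 reading that value would also meet the 25% site alert in Appendix 6, although a second peak of 2.0 would not. What remains is that none of these is a laboratory count by arm. The visible SAP also passes from 2.7 to 2.11, so a renal analysis against the reference creatinine may exist in withheld sections.

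**Resolution is not an analysis.** A reader might infer that the trial will report a return to the AKI level as resolved. The rule only ends site monitoring, the visible SAP does not tabulate it, and its baseline is unnamed.

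**Mineralization.** The preclinical finding, "Minimal to mild perivascular/vascular mineralization in kidney, reproductive tract and thyroid", suggests a renal safety link, but a weak one: that risk is followed through calcium, phosphorus and pyrophosphate and counted separately as an event of special interest.

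**White cells and platelets.** A white cell count falling from 22 to 10 as sepsis clears is −54.5% and is flagged. A reader might infer that the table counts recovery as harm and should be limited to out-of-range values. A flagged value is not automatically an adverse event, and the limit would have a price: platelets falling from 320 to 155 (−52%) would drop out if the lower limit of normal is 150 (assumed), although bleeding is an event of special interest.

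**Conclusion.** The point holds in limited form. Under the SAP's default baseline, the Table 2-2 creatinine count misses a second kidney injury after recovery up to 1.5 times Day 1: 2.25, 3.0 and 4.5 times reference when Day 1 is 1.5, 2 and 3 times reference. This rests on Day 1 being the comparator, which follows from SAP 2.1.1 but is not stated in the table. How many participants would recover and be injured again cannot be estimated from the documents. The gap is confined to one supplementary safety row; the primary PK analysis is unaffected.

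Appendix 6 is a separate inconsistency. Its baseline is undefined, neither candidate fits all of its text, and its stabilization window is longer than follow-up. Which clinical rule should apply is for the sponsor.

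**What to change.** **SAP 2.6.1 and Table 2-2.** Name Day 1 as the creatinine comparator. Beside that row add, by arm, the number of participants with a rise above 50% from the lowest earlier post-dose creatinine, identifying values obtained during or shortly after RRT. State whether the count uses local or central creatinine: Protocol 8.4 schedules local chemistry at fewer visits than the central samples in 8.3.1.

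**Reference creatinine.** If a comparison with it is shown, present it as a shift from the Day 1 category. A plain count would include everyone who entered above 1.5 times reference and so record the qualifying AKI as a new event.

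**White cells and platelets.** Keep the existing counts. Optionally show separately which flagged values are outside the normal range.

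**Protocol Appendix 6.** Ask the sponsor to state which baseline each alert and the resolution rule use, and to reconcile 10.6 to 10.6.1.1 with the baseline definitions in Protocol 9.2.1 and SAP 2.1.1, with Table 8-1 and with the 90-day follow-up.

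**Cost.** Some programming on data already collected, a few rows in one table, and a wording correction. The added row will pick up some rebound after RRT, and it needs to be read beside the Day 1 row because early worsening of the qualifying AKI can also enter it.

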2.6.2 Sensitivity analyses

[figure not shown]
Not applicable.

2.6.3 Supportive analyses

Not applicable.

2.7 Safety analyses

Please refer to [Section 2.6](#).

2.11 Interim analysis

An interim analysis is planned when approximately 8 patients complete Day 14 visit. The study will continue to recruit participants while this interim analysis is being completed up to a cap of 12 participants. The study will continue without modification if a similar PK profile of TIN816 to that in the healthy volunteers (CTIN816A02101) is confirmed. Otherwise, the study may be amended with options of additional arms for testing a higher dose, multiple bolus doses, extended infusion dosing regimens or combination of bolus dose and extended infusion. The total sample size may increase to provide adequate PK data after dose level and/or dose regimens are changed. In the circumstance that the data from the first IA does not provide sufficient PK data to support the phase 2b, an additional IA will be added when all 20 patients complete Day 14 visit.

3 Sample size calculation

3.1 Primary endpoint

The sample size was determined to achieve a target margin of error of the mean for PK parameters C_{max} and AUC_{inf} . The assumption of geometric coefficient of variation (GCV) rate was referenced from FIH study (CTIN816A02101) interim safety report.

The proposed sample size of 15 participants in TIN816 study treatment arm is sufficient to achieve a target margin of error not larger than 15% of the geometric mean (half-width of a 2-sided 95% confidence interval for the PK parameters) assuming geometric coefficient of variant (GCV) is 0.25 in AUC_{inf} or C_{max} . It will also be able to exclude a 1.5-fold change in AUC_{inf} or C_{max} assuming GCV increased variability of 0.75.

Different GCV rates and corresponding precision of confidence interval are shown in below table.

Table 3-1 Sensitivity of confidence interval precision to change in assumption for GCV rate

GCV rate *	Width of 95% confidence interval
0.25	[geometric mean/1.15, geometric mean x 1.15]
0.50	[geometric mean/1.31, geometric mean x 1.31]
0.75	[geometric mean/1.47, geometric mean x 1.47]

*Geometric mean of AUC_{inf} and C_{max} for 2 mg/kg are 8% and 22%, respectively in FIH study (CTIN816A02101) interim safety reports

3.2 Secondary endpoints

Not applicable.

4 Change to protocol specified analyses

Pharmacokinetic parameters from non-compartmental analysis in [Table 2-1](#) are normalized by actual dose.

Treatment emergent adverse event will not be summarized by treatment, SMQ and preferred term.

5 Appendix

5.1 Imputation rules

5.1.1 AE date imputation

AE end date imputation

Rules for imputing AE end dates are stated below. Date of last contact in the study has been defined as in [Section 2.1.1](#).

1. If the AE end date month is missing, the imputed end date should be set to the earliest of the (date of last contact, 31DECYYYY, date of death).
2. If the AE end date day is missing, the imputed end date should be set to the earliest of the (date of last contact, last day of the month, date of death).
3. If AE year is missing or AE is ongoing, the end date will not be imputed.

AE start date imputation

Rules for imputing the AE start date:

The following table explains the notation used in the logic matrix. Please note that **missing start dates** will not be imputed.

	Day	Month	Year
Partial Adverse Event Start Date	Not used	MON	YYYY
Treatment Start Date	Not used	TRTM	TRTY

The following matrix explains the logic behind the imputation.

	MON MISSING	MON < TRTM	MON = TRTM	MON > TRTM
YYYY MISSING	(1) No convention			
YYYY < TRTY	(2.a) Before Treatment Start	(2.b) Before Treatment Start	(2.b) Before Treatment Start	(2.b) Before Treatment Start
YYYY = TRTY	(4.a) Uncertain	(4.b) Before Treatment Start	(4.c) Uncertain	(4.c) After Treatment Start

YYYY > TRTY	(3.a) After Treatment Start	(3.b) After Treatment Start	(3.b) After Treatment Start	(3.b) After Treatment Start
-------------	-------------------------------------	-------------------------------------	-------------------------------------	-------------------------------------

Before imputing AE start date, find the AE start reference date.

1. If the imputed AE end date is complete and the imputed AE end date < treatment start date then AE start reference date = min(informed consent date, earliest visit date).
2. Else AE start reference date = treatment start date

Impute AE start date -

1. If the AE start date year value is missing, the date uncertainty is too high to impute a rational date. Therefore, if the AE year value is missing, the imputed AE start date is set to NULL.
2. If the AE start date year value is less than the treatment start date year value, the AE started before treatment. Therefore:
 - a. If AE month is missing, the imputed AE start date is set to the mid-year point (01JulYYYY).
 - b. Else if AE month is not missing, the imputed AE start date is set to the mid-month point (15MONYYYY).
3. If the AE start date year value is greater than the treatment start date year value, the AE started after treatment. Therefore:
 - a. If the AE month is missing, the imputed AE start date is set to the year start point (01JanYYYY).
 - b. Else if the AE month is not missing, the imputed AE start date is set to the later of (month start point (01MONYYYY), AE start reference date + 1 day).
4. If the AE start date year value is equal to the treatment start date year value:
 - a. And the AE month is missing the imputed AE start date is set to the AE reference start date + 1 day.
 - b. Else if the AE month is less than the treatment start month, the imputed AE start date is set to the mid-month point (15MONYYYY).
 - c. Else if the AE month is equal to the treatment start date month or greater than the treatment start date month, the imputed AE start date is set to the later of (month start point (01MONYYYY), AE start reference date + 1 day).

If complete imputed AE end date is available and the imputed AE start date is greater than the imputed AE end date, then imputed AE start date should be set to the imputed AE end date.

